This is a minimal risk study using a behavioral intervention to enhance HIV-related health behaviors and biomedical outcomes. The PI will be working with engaged staff at the University of North Carolina Global Projects Zambia (UNC GPZ) to implement the study. The proposed study uses a randomized controlled trial design (Phase II clinical trial) to test the efficacy of a couples counseling and health education intervention to change HIV-related health behaviors and biomedical outcomes (viral suppression) among pregnant and postpartum women living with HIV in Lusaka, Zambia. Our sample includes 238 heterosexual couples (n=476 individuals) recruited from the population of pregnant women living with HIV attending antenatal care at Chipata Clinic in Lusaka, Zambia. All enrolled couples (intervention and control groups) will be exposed to two group health education events. Couples in the intervention (n=119 couples) will additionally be exposed to three couples counseling visits. Biospecimen collection will take place in the form of three research-only blood draws to test viral loads among the female participants (n=238). We will also conduct face-to-face behavioral interviews using a standardized questionnaire. Recruitment and initial screening will take place during routine antenatal care (see Figure below). Local Zambian research assistants will work with nurses (relationship already established during the K99 phase) to conduct the initial screenings and recruit participants. Research assistants will arrange with interested, eligible women a convenient time and place to meet with them and their male partners (either the clinic or a private community venue) to complete the informed consent process, full screening, and enrollment. A letter will be offered to take home to the male partner explaining the study (women's HIV status will not be conveyed). Screening and informed consent will be done in separate locations for WLWH and their male partners (preferably at the same time) with gender-matched research assistants. Women with severe IPV will be offered support and referrals but will not be enrolled. Enrolled couples

will attend the first group education session (“baby shower” event) together during an upcoming weekend. Randomization into the intervention or control (n=119 couples per arm) will take place following the first group session using labeled envelopes.

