Procedures: We will schedule a series of 24 group education sessions across three months to take place on the weekends at community venues with an expected 10 couples in each group. The first baseline behavioral questionnaire will be administered during the group education session. All research assistants will be present at the scheduled group sessions to assist with the educational activities and administer the behavioral questionnaires. At this same time, we will collect baseline viral loads of pregnant WLWH. Couples in the intervention arm will subsequently receive three additional couples counseling sessions at a private community venue or the clinic (depending on participant preference): one during pregnancy (3rd trimester) and two postpartum (12 weeks and 18 weeks). Lay health workers will deliver the intervention and be supervised by a local study coordinator and the PI throughout the entirety of the project. The paired male-female counselors will work with each couple in the intervention. At 6 weeks postpartum, there will be a series of second group education sessions for all couples (intervention and control arms) and the mid-line behavioral questionnaire. The mid-line viral load will also take place at 6 weeks postpartum. At 24 weeks postpartum, we will collect the end-line behavioral questionnaires and viral load. Once data collection is complete, we will offer couples in the control arm the option to participate in a condensed (one-session) counseling intervention. We will not be assessing outcomes in the condensed intervention but thought it ethical to provide.

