the procedure; and 5) risks associated with participation in the intervention activities (group education sessions and/or couples counseling visits). Pregnant and postpartum women and infants also face risks of adverse pregnancy outcomes (e.g., preterm birth, miscarriage) and infant/maternal mortality, which are common in the study community but are not likely to be related to study participation but will be monitored during the course of the study. There is one exception to confidentiality: this study does not anticipate any mandatory reporting information being revealed in the course of the study; however, if child abuse is disclosed, Zambian law requires a report to law enforcement. Detailed protocols will be in place regarding the possibility of tension, conflict or violence between partners during or outside the counseling sessions. Protocols will be in place to monitor and respond to any instances reported by the participants of any type of negative relationship or other social event, and proper action will be taken, including the provision of referral for services depending on the specific event and participant preferences.

Safety-monitoring procedures: All safety-related risks will be monitored routinely, including during recruitment and enrollment, intervention sessions, and data collection (questionnaires, medical record reviews, and biospecimens). All participants will complete an informed consent process emphasizing their rights and the voluntary nature of the study, which will be read aloud from an information sheet (due to low literacy levels in the target population) and followed by participant signature/thumbprint. The intervention has been carefully designed to minimize conflict within couples and ensure privacy, including protecting confidential information (e.g., HIV status) from one's partner and to monitor all confidential information to protect subject privacy and inadvertent social harms. During study procedures, at any sign of participant discomfort or distress, or by request, the activity will be halted and applicable support and referrals (e.g., mental health or domestic violence services) will be provided. Confidentiality will be assured to all participants at the time of consent; they will be assured their answers or responses cannot be used against them for any reason, or for denial of any medical treatment.

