Safety-related risk reporting and action plan: The PI will be responsible for executing the DSMP, conforming to rigorous standard monitoring procedures for participant safety, and complying with reporting requirements. The PI has primary responsibility for the overall conduct of the study, including the safety of human subjects. The PI will ensure appropriate (1) conduct of the informed consent process (e.g. that informed consent is obtained before proceeding with study procedures); (2) enrollment of study subjects; (3) collection and analysis of data; (4) implementation of study procedures to ensure consistent monitoring of subjects for possible adverse events; (5) immediate receipt and review of standardized and detailed adverse reports and reporting of to the Institutional Review Boards; and (6) maintenance of the privacy and confidentiality of study subjects. The PI will be in contact with the local Zambian research team (calls biweekly) throughout the study to review progress and address any human subject safety concerns. The PI will also review all electronic study data monthly from REDCap to ensure that the DSMP and all protection of human subject protocols are followed. The PI will conduct in-person reviews of the study procedures and data collection biannually in Lusaka. If any increased risks are identified during the study, the PI will review and determine the adequacy of human subject protections, making recommendations for enhancing these protections if deemed necessary.

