Any adverse events, serious adverse events, unanticipated problems involving risks to subjects, or other participant safety or data concerns will be reported to the on-site study coordinator and the PI by study staff within 48 hours of becoming aware of the event. Serious adverse events that could be related to the study and any study deaths (extremely unlikely) will be reported by the PI to the NIMH Program Officer immediately. In addition to serious adverse events, the following will be reported by the PI to the NIMH Program Officer: unanticipated problems involving risks to subjects, protocol violations (significant divergences from the IRB-approved protocol), non-compliance, and suspensions or terminations by monitoring entities (IRBs and the Zambian National Health Research Authority). Non-serious adverse events and unrelated serious adverse events will be reported in the annual progress report to NIMH. The PI will oversee follow-up on any safety concerns that arise and work with the Study Coordinator to ensure that participants in need of medical, legal, or psychosocial services receive

appropriate, timely referrals. The PI will adhere to the NIMH Reporting Policy (<https://www.nimh.nih.gov/funding/clinical-research/nimh-reportable-events-policy.shtml>).

E. Potential Scientific Problems:

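### Social harms and non-serious adverse events are picked up at contacts, and the counselling arm has five scheduled contacts after randomisation against two for control, so counts tabulated by arm may differ at equal true rates.

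*Combined protocol and SAP*

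**What the plan says.** Section IV.D, under Safety-monitoring procedures, states: "All safety-related risks will be monitored routinely, including during recruitment and enrollment, intervention sessions, and data collection". A bracket then names questionnaires, medical record reviews and biospecimens as the data-collection sources. The same part of IV.D promises a response to negative relationship or social events that participants report. Under the risk reporting and action plan, adverse events and other safety concerns "will be reported to the on-site study coordinator and the PI by study staff within 48 hours of becoming aware of the event". Both routes depend on someone disclosing or noticing an event.

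The schedule is in Section IV.C. "Randomization into the intervention or control (n=119 couples per arm) will take place following the first group session using labeled envelopes". The baseline survey is also given at that session ("The first baseline behavioral questionnaire will be administered during the group education session"), so neither is a contact after randomisation. Then: "Couples in the intervention arm will subsequently receive three additional couples counseling sessions", one in the third trimester and the others at 12 and 18 weeks postpartum. Both arms are next seen six weeks after birth, when "there will be a series of second group education sessions for all couples (intervention and control arms) and the mid-line behavioral questionnaire". End-line data are collected from both arms at 24 weeks. The condensed session offered to controls comes after data collection has ended.

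Section IV.D makes the PI responsible for consistent adverse-event monitoring, but gives no contact schedule, common question set or record of where an event came to light. It adds: "If any increased risks are identified during the study, the PI will review and determine the adequacy of human subject protections". That sentence does not mention arms. The analysis table in Section IV.F has no comparison of adverse events or social harms by arm. Partner violence appears there only as a survey-measured mechanism with past-month recall.

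**The concern.** When detection depends on contact and one arm has more contacts, the recorded count reflects both how often harm occurs and how often anyone looks. The widest gap is between 6 and 24 weeks postpartum. Controls have no scheduled contact for 18 weeks, while counselling couples have two 90-minute sessions, one of which covers resolving conflict without violence. Tension, conflict or violence between partners is one of the safety risks listed in Section IV.D, and these sessions are where it could well be disclosed.

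The trial may enrol women who have experienced partner violence, and Section IV.G says it will support a larger trial. Someone is likely to set the harms side by side. An excess under counselling could then be a product of more looking, and a real excess could be explained away on the same ground. Once the data are in, events found under unequal observation cannot be put on a common footing.

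**Working it through.** **The plan's own figure.** No figure for harms is given. The illustration below uses the enrolment figure from Section IV.F, which reproduces: 55% v 75%, two-sided 5% test, 80% power gives 89 per arm (178), and 178 / (1 − 0.25) = 237.3, rounded up to 238, or 119 per arm.

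**Contacts after randomisation (Section IV.C).**

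| Contact | Counselling | Control |
|---|---|---|
| Counselling visit 1, third trimester | yes | no |
| 6 weeks postpartum | yes | yes |
| Counselling visit 2, 12 weeks | yes | no |
| Counselling visit 3, 18 weeks | yes | no |
| 24 weeks postpartum | yes | yes |
| Total | 5 | 2 |

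If blood draws at the hospital laboratory are separate attendances, each arm gains two (7 v 4). The excess of three is unchanged.

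**Assumptions not in the documents.** True harm rates are equal. Harms are spread evenly from 8 weeks before birth to 24 weeks after (32 weeks). Counselling visit 1 falls 4 weeks before birth.

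**(a) Fixed recall window.** The share detected is the share of the 32 weeks lying within the window before some contact.
- 4 weeks: control 2 × 4 / 32 = 25%; counselling 5 × 4 / 32 = 62.5%; ratio 2.5.
- 12 weeks: control 2 × 12 / 32 = 75%; counselling 100%, as its windows overlap; ratio 1.33.
- 18 weeks or more: both 100%; ratio 1.0.

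**(b) Detection probability p at each later contact, with carry-over.** A harm with m contacts still to come is found with probability 1 − (1 − p)^m. At p = 0.5:
- Control: 14 weeks with m = 2 and 18 weeks with m = 1, so (14 × 0.75 + 18 × 0.5) / 32 = 19.5 / 32 = 0.609.
- Counselling: (4 × 0.96875 + 10 × 0.9375 + 6 × 0.875 + 6 × 0.75 + 6 × 0.5) / 32 = 26 / 32 = 0.8125.
- Ratio 0.8125 / 0.609 = 1.33.

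Other values of p: 0.10 gives 1.89, 0.25 gives 1.65, 0.75 gives 1.13, 0.90 gives 1.04, and 1.0 gives 1.0.

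**Sensitivity.** Starting 12 weeks before birth (visit 1 at 6 weeks before) or 4 weeks before (visit 1 at 2 weeks before) gives 2.5 and 2.25 for the 4-week window, and 1.32 and 1.34 for p = 0.5. The range stays at 1.0 to 2.5.

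**Illustrative counts.** Assume a true harm rate of 20% in both arms, so 0.20 × 119 = 23.8 couples per arm, with no allowance for loss to follow-up. The last column is the chance of a nominally significant difference in a two-sided 5% two-proportion test.

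| Detection | Counselling | Control | Chance |
|---|---|---|---|
| Complete | 23.8 | 23.8 | 5% |
| p = 0.5, carry-over | 23.8 × 0.8125 = 19.3 | 23.8 × 0.609 = 14.5 | 15% |
| 4-week recall | 23.8 × 0.625 = 14.9 | 23.8 × 0.25 = 5.95 | 56% |

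**With harms elicited only at 6 and 24 weeks, using the same questions in both arms.** Contacts are 2 v 2, and the expected ratio is 1.0 under the same assumptions.

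**The case against.** The strongest reply is that the plan contains no comparison to bias. Section IV.F compares no adverse events or social harms by arm, and Section IV.D describes individual reporting, referral and annual listing. That stands, and it confines the point to what happens when harms are tabulated or interpreted by arm.

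Second, partner violence is already surveyed in both arms at baseline, 6 and 24 weeks, and the safety manager's follow-up of reported violence or major depression is triggered by those surveys. This also stands. Past-month recall leaves 14 of the 18 weeks between the two postpartum surveys unobserved, but equally in both arms. A reader might infer that no safety signal from this trial could be interpreted; the common survey schedule shows that this goes too far.

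Third, medical record reviews need not depend on counselling visits, and maternal or infant death and preterm birth are unlikely to be missed by 24 weeks. The point is therefore about disclosed or noticed social harms and non-serious adverse events.

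Fourth, a reader might take Sections IV.D and IV.E to make the absence of extra social harm a claim that this trial tests. Both passages cite earlier studies to justify the risk. It is not an aim, hypothesis or outcome here.

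Finally, confining every comparison to commonly elicited events could hide harms caused by the sessions themselves, which Section IV.D lists as a risk. That objection is sound, and the change below allows for it.

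**Conclusion.** The imbalance of five scheduled contacts against two is read directly from the schedule, and nothing in the plan equalises elicitation or records where an event was found. If harms are tabulated by arm, counts may be higher under counselling at equal true rates. Under the assumptions shown, the ratio of detected harms lies between 1.0 and 2.5; the documents do not allow a narrower range.

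Two stronger readings are not supported. One is that counts are bound to differ: with complete capture, or recall of 18 weeks or more at the common assessments, they need not. The other is a near-certain false signal. A reader could compare 1 − (1 − p)^5 with 1 − (1 − p)^2, which at p = 5% gives 22.6% v 9.8% and a 77% chance of a nominally significant difference with 119 per arm. That formula has no true event rate and lets nothing missed at one contact be found at the next, so it lies towards the worst case.

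The primary outcome is untouched. The gap is worth closing before data collection because it cannot be repaired afterwards.

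**What to change.** Leave individual event reporting as it is. Then:

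- In Sections IV.D and IV.F, add the same structured harm questions for both arms at the existing 6- and 24-week surveys, with recall reaching back to the previous assessment. A past-month window would not do this.
- Add a REDCap field for where each event was first found: common assessment, counselling visit or other.
- State in Section IV.F that the main by-arm comparison of harms uses the commonly elicited events. Also show all events by arm, split by source, so that harms found only at counselling visits stay visible.

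The cost is a few survey questions, one data field and one extra table, with no new visits. The change equalises the opportunity to report. It cannot guarantee equal willingness to disclose, and recall over 18 weeks will be imperfect, though the window is the same in both arms.

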The informed consent process will explain all study procedures and include the following: why the study being done; how many people will take part in the study; why they have been chosen to participate in the study; what will happen if they take part in the study; how long they will be in the study; if they can stop being in the study; what side effects or risks to expect from being in the study; benefits to taking part in the study; their choices if they do not take part in the study; how information will be kept private; the costs of taking part in the study; payment and compensation for taking part in the study; their rights if they take part in the study; and who can answer questions about the study. Participants will have the opportunity to ask questions and voluntary participation will be emphasized. After this information is conveyed to the participant, they will be asked to sign a statement indicated they provide consent to participate.

Numerous studies indicate that couples' counseling within HIV interventions do not result in increased social harms. Nonetheless, careful effort has been made to minimize, monitor, and address potential social harms. The intervention has been designed to minimize conflict within couples and ensure privacy. First, women's HIV status will not be conveyed to the male partner (or anyone outside the study team). Second, couples in the intervention group will select the location (clinic or community venue) they feel most comfortable to have the couple counseling sessions. Third, because we are including women who have potentially experienced IPV, all activities have been designed in accordance with the WHO recommendations for conducting research on violence against women. A local safety monitoring manager in Lusaka will be hired to monitor data and any adverse events. He/she will follow-up with any participants who report IPV or major depression on the behavioral questionnaires and offer referrals to medical, legal, or psychosocial services.

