Data-related risk reporting and action plan: We will closely track incoming numbers of participants via ongoing recruitment activities, and weekly and monthly progress reports will be compiled by the study staff and reviewed by the Study Coordinator and the PI. We will utilize similar procedures to monitor any missing data. Recruitment and missing data reports will be monitored weekly by the Study Coordinator and monthly by the PI. All data will be protected on firewall-protected servers at the University of Colorado. Any identification of recruitment rates or follow-up rates that represent threats to our ability to sufficiently answer the research questions will be met with action by the PI to intervene to remedy the shortcomings, including adding additional recruitment sites (antenatal clinics). Should a situation arise of insufficient power or early detection of research questions, the PI will review and discuss with NIMH halting the study, when and if needed, and would report such action to all monitoring bodies. Completion rates of intervention activities will be monitored in parallel fashion using study logs.

Safety-related risks: Safety-related risks to participants could consist of: 1) emotional discomfort or distress resulting from sensitive questions being asked on the behavioral questionnaires pertaining to HIV and/or relationship issues; 2) social risk (e.g. risk to reputation) if confidential information revealed during the course of the study were to be disclosed outside of the research team; 3) tension, conflict or violence between the partners 4) risks related to biospecimen collection (research-only blood draws), such as physical discomfort, and the unlikely potential for infection or other physical repercussions from

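### The stated safety provisions act on single events: no by-arm review of partner violence is described while counselling runs, and the study team's only study-level halting ground is power or early detection

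*Combined protocol and SAP*

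**What the plan says.** Section IV.D has two separate action plans. Under data-related risks: "Should a situation arise of insufficient power or early detection of research questions, the PI will review and discuss with NIMH halting the study". Under safety-related risks: "If any increased risks are identified during the study, the PI will review and determine the adequacy of human subject protections", after which the PI may recommend strengthening them. The second passage mentions neither a halt nor a discussion with NIMH.

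Other safety provisions surround these. During study procedures, "at any sign of participant discomfort or distress, or by request, the activity will be halted", with support and referral. For partner conflict, "Detailed protocols will be in place regarding the possibility of tension, conflict or violence between partners during or outside the counseling sessions", but their content is not given. "A local safety monitoring manager in Lusaka will be hired to monitor data and any adverse events"; this person follows up individuals who report IPV or major depression. Staff report events to the coordinator and PI within 48 hours, and the PI reports to the ethics boards. Possibly related serious events and deaths go to NIMH at once, and unanticipated problems are also reported there. "Non-serious adverse events and unrelated serious adverse events will be reported in the annual progress report to NIMH". The ethics boards and the Zambian authority are recognised as able to suspend or terminate the study. "The PI will also review all electronic study data monthly from REDCap"; the stated purpose is to confirm that the monitoring plan and the protection protocols are followed.

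**The concern.** The plan itself lists conflict or violence between partners among the study's safety risks. It notes in Section II that pregnancy can increase conflict in some couples, and it enrols couples with IPV unless it was severe in the past six months. Joint counselling could lower violence or raise it. A rise in one arm is a difference between groups, and reviewing reports one at a time does not reveal it. IPV otherwise appears only as an Aim 2 mechanism for mediation analysis, with no comparison described during the trial.

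Two things are at stake. One is the safety of couples still to be counselled if early couples show an excess. The other is the trial's ability to check, as it runs, the prior evidence of no increased social harm on which Sections IV.D and IV.E rely.

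**Working it through.** **The plan's own figure.** Section IV.F.2 gives 55% versus 75% suppression, alpha 0.05, power 0.80 and 25% loss. Two-sided and without continuity correction:

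n per arm = [1.960·√(2·0.65·0.35) + 0.842·√(0.55·0.45 + 0.75·0.25)]² / 0.20² = 88.1, rounded up to 89.

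2 × 89 = 178 evaluable couples; 89 / 0.75 = 118.7, so 119 per arm and 238 in total. This reproduces the plan. The point does not depend on it, but it supplies the arm sizes used below.

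**Safety and halting provisions side by side (all Section IV.D).**

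| Provision | Acts on | Arms compared? | Leads to |
|---|---|---|---|
| Halt for distress or on request | One participant | No | Support, referral |
| Safety manager's follow-up of IPV reports | One participant | None stated | Referral |
| Violence protocols | Content not given | None stated | Action and referral by event |
| 48-hour reporting; reports to ethics boards and NIMH | Single events | None stated | Notification |
| Annual report to NIMH | Non-serious and unrelated serious events | None stated | Notification |
| PI's monthly data review | All study data | None stated | Compliance check |
| Outside suspension or termination | Whole study | No criterion stated | Suspension |
| Increased risk identified | Whole study | None stated | Recommendations |
| Insufficient power or early detection | Whole study | Not a harm | Halting discussion with NIMH |

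Only the last row gives the study team a route to a halting discussion. No row assigns a comparison of harm between arms.

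**Timing within a couple.** Counselling is in the third trimester and at 12 and 18 weeks postpartum (Section IV.C, Procedures). Surveys are at baseline, 6 and 24 weeks, and the analysis table in Section IV.F lists IPV over the past month. Taking a month as four weeks, the two postpartum surveys cover about weeks 2 to 6 and 20 to 24. Only the 6-week survey falls during counselling, before visits 2 and 3. Weeks 6 to about 20, which contain both those visits, lie in neither window.

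**Timing across couples.** Assume birth at 40 weeks. A couple enrolled in study week 0 near the 36-week limit has its surveys at weeks 4 + 6 = 10 and 4 + 24 = 28. A couple enrolled at the same gestation at the end of a 13-week session series has visit 3 at week 13 + 4 + 18 = 35. Survey data from early couples therefore exist while later couples are still being counselled.

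**What a comparison could detect.** The control-arm rate p₁ is an assumption (10, 20, 30, 40 and 60%). With excess d, p₂ = p₁ + d, and p̄ the mean of p₁ and p₂, for two-sided alpha 0.05:

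power = Φ{[d√n − 1.960·√(2p̄(1 − p̄))] / √(p₁(1 − p₁) + p₂(1 − p₂))}.

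Example: p₁ = 0.40, p₂ = 0.50, n = 119 gives (1.091 − 1.379) / 0.700 = −0.41, so power is 34%.

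| Per arm | 10-point excess | 15-point | 20-point |
|---|---|---|---|
| 119 (no loss) | 34.0–58.0% | 64.1–86.6% | 87.5–97.5% |
| 89 (25% loss) | 26.7–46.3% | 51.8–75.4% | 76.5–92.2% |

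These are for one comparison with every couple contributing. A table made partway through accrual has less power.

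**The case against.** Several objections stand. The plan does more than issue recommendations, as the table shows. The monitoring plan and violence protocols are named but not included, so one can say only that no by-arm review is stated here. The two action plans cover different kinds of risk and do not contradict each other; the fault is an asymmetry. In a pilot described as minimal risk, by-arm harm monitoring is partly a matter of judgement. Intervention couples also have three extra counsellor contacts, so spontaneous reports could rise in that arm through ascertainment alone.

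A reader might infer three stronger conclusions, which the documents do not support:

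- *No safety finding could stop the trial.* Outside bodies can suspend it, and the unseen protocols may say more.
- *With IPV above 60%, any single report would pass as background, and expected counts follow from that rate.* The 60% comes from an earlier study with no recall period given. This trial excludes recent severe IPV and measures the past month, so no expected count can be derived.
- *The annual report to NIMH would arrive after all counselling.* That rests on 24 sessions of 10 couples in three months, but the COVID-19 section caps group sessions at 10 people including staff. With two facilitators, that is 4 couples per session and 238 / 4, or about 60 sessions. At the same pace this takes 60 / 24 × 13 = 32.5 weeks, which puts the last visit 3 at 32.5 + 4 + 18 = 54.5 weeks even for enrolment at 36 weeks' gestation. The report's date is not tied to enrolment either.

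None of this supplies a between-arm review or a safety route to a halting discussion.

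**Conclusion.** The point holds as a gap in what is stated. Safety provisions operate on individual events or give no criterion; no by-arm review of partner violence is described during counselling; and the study team's only study-level halting ground is not a safety ground. This is an inexpensive improvement to participant protection and does not affect the validity of the primary analysis. No expected number of excess events can be given. The detectability figures rest on assumed control rates and complete data; they show that a review would mainly catch excesses near 20 points and would often miss one of 10. The past-month recall limits it further, because the period around visits 2 and 3 is largely unobserved by survey.

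**What to change.** 1. Reconcile the two action plans in Section IV.D so that an identified safety risk has at least the same route to a halting discussion, with NIMH and the ethics boards, as insufficient data.
2. Add to the monthly REDCap review cycle a by-arm tabulation of IPV and serious social harms, stating who prepares it, from which data, and who receives it. Limit access to the safety monitoring manager and the recipients of a referral.
3. Base the table mainly on the 6- and 24-week surveys, which both arms complete on the same schedule and which accrue on a rolling basis. Show spontaneous reports separately because of the extra contacts in the intervention arm.
4. Leave any referral criterion to the sponsor and ethics boards; none is proposed here.

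The cost is protocol and monitoring-plan wording plus one monthly table from data already collected. The downsides are that harm data are seen by arm during the trial, that smaller excesses will usually be missed, and that the survey windows leave a gap around the later counselling visits. No new committee or extra visit is needed.
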